Real-Time Continuous Glucose Monitoring to Aid Weight Loss in Prediabetes

IRB Protocol Number: 49402

NCT Number: 03844646

Table of Contents

STUDY OVERVIEW	3
KEY STUDY PERSONNEL.....	4
FUNDING SOURCES.....	4
Study Protocol.....	5
1. BACKGROUND.....	5
2. STUDY AIMS	6
3. STUDY DESIGN.....	7
3.1 Sample Size	7
3.2 Study Population.....	7
3.3 Study Location.....	7
3.4 Study Duration	7
3.5 Randomization	7
4. STUDY PROCEDURES	8
4.1 Study Design.....	8
4.2 Recruitment	8
4.3 Intervention	8
5. STATISTICAL CONSIDERATION	9
5.1 Statistical Basis for Sample Size	9
5.2 Statistical Plan	9
REFERENCES	10
APPENDIX	12
A. Inclusion/exclusion criteria.....	12
B. Questionnaire	12
C. Outcome Measurement Methods	13

STUDY OVERVIEW

Study Title

Real-Time Continuous Glucose Monitoring to Aid Weight Loss in Prediabetes

Abbreviations

Real-Time Continuous Glucose Monitoring (RT-CGM)

Study Aims and Outcome Measures

RT-CGM has revolutionized the treatment of patients on intensive insulin therapy and its utility can also be harnessed to help individuals with prediabetes make healthful lifestyle changes. Successful weight loss requires adherence to lower calories, regular exercise, and self-monitoring. This proposal will test the hypothesis that RT-CGM will facilitate all of these components for successful weight loss by functioning as a continuous self-monitor and guiding healthful food choices and physical activity.

AIM #1: Compare weight loss.

Intermittent RT-CGM use will augment dietitian-guided weight loss in individuals with prediabetes.

AIM #2: Compare physical activity.

Intermittent RT-CGM use will increase physical activity compared with dietitian support only.

[figure not shown]
Other measures will include glucose indices (fasting glucose, A1c).

Study Population

We aim to enroll 50 participants who are overweight/obese with prediabetes. Please see [APPENDIX A](#) for more detailed inclusion/exclusion criteria.

Design

This will be a randomized, parallel-group, pilot study of intermittent RT-CGM with dietitian support versus dietitian support only.

Duration

We anticipate that the entire study will take 24 months through data analysis. Each eligible candidate who voluntarily consents to participate in the study will be active on the study for a total of 4 months.

KEY STUDY PERSONNEL

Co-Principal Investigator

[name] MS

Associate Professor of Medicine, Division of Endocrinology, Stanford University

Co-Principal Investigator

[name]

1. BACKGROUND

The heart of diabetes prevention is lifestyle changes and weight reduction. The pivotal Diabetes Prevention Program (DPP) study clearly demonstrated that weight loss of 7% and moderate physical activity reduced the incidence of type 2 diabetes (DM2) in individuals with prediabetes.¹ In addition, lifestyle changes were superior to early initiation of metformin, a glucose-lowering medication. While benefits of lifestyle changes are undeniable, successful interventions are lacking to help individuals with prediabetes make and sustain lifestyle changes leading to significant weight loss. Currently, DPP-modelled “real-life” interventions show an average weight loss of 4% and show drop-out rates as high as 50%.²

The goal of this proposal is to test the hypothesis that **real-time continuous glucose monitoring (RT-CGM) will facilitate weight loss in overweight/obese individuals with prediabetes**. Although controversy exists regarding optimal diets and interventions for weight loss, there is consensus that the following components are generally needed to lose weight:³ 1) reduction in energy intake, 2) participation in physical activity and 3) incorporation of self-monitoring (e.g., food tracking). We hypothesize that RT-CGM will help the user achieve all of these components and lose weight. Unlike other health trackers which relies on user input, RT-CGM provides continuous monitoring and instantaneous feedback on glucose levels which reflect user food choices and physical activity. A small sensor is inserted below the skin and into the interstitial fluid. The sensor measures glucose from 40 to 400mg/dL every 5 minutes and transmits the data wirelessly to a display such as a smart phone (Fig. 1). Eating generally increases and exercise decreases glucose concentrations. As individuals with prediabetes have some degree of insulin secretory dysfunction and hyperglycemia, certain food choices (high in carbohydrate content, added sugars, and calories) may increase glucose more than other healthful choices. Thus, RT-CGM can monitor when eating is occurring and also can provide feedback on the effect of food choices to adversely increase glucose. Furthermore, it can also reflect the beneficial effects of exercise to lower glucose. Thus, coupled with education, we hypothesize that RT-CGM can be used as a self-monitoring device to motivate healthful food choices and physical activity that maintain lower glucose and aid weight loss.

RT-CGM is an existing technology that is being underutilized. There has been little direct examination of RT-CGM as a behavior modification and weight loss tool in individuals with prediabetes. CGMs currently are indicated for patients treated with intensive insulin therapy such as those with type 1 diabetes.⁴ Use of CGM in individuals with type 1 diabetes has been consistently shown to improve glucose control.^{5,6} In limited studies in patients with DM2, use of CGM also has been successfully used to motivate behavioral change and weight loss.⁷ The potential benefits of CGM also are suggested by studies of activity monitors in the general population.⁸ Collectively, those individuals most adherent with tracking food, activity and weight show the greatest weight loss.⁹ With this understanding, RT-CGM may function as the ultimate self-monitoring device as instantaneous glucose changes will reflect effects of food choices and physical activity.

Fig 1.
Glucose
readings from
RT-CGM
displayed on a
smart phone
can be used to
motivate food
choices and
physical

The goal of this proposal is to assess whether **RT-CGM will augment dietitian-guided weight loss and influence food choices and physical activity in overweight/obese patients with prediabetes**. In essence, we will be evaluating whether CGM can function as the ideal self-monitoring device.

Study Rationale

Currently, over a third of adults qualify for the diagnosis of prediabetes,¹⁰ and 5-10% of those with prediabetes progress to DM2 every year.^{1,11} Lifestyle changes and weight loss significantly delay the progression to DM2.¹ However, weight loss remains challenging and newer tools are desperately needed to help overweight/obese individuals with prediabetes change lifestyle and lose weight.

RT-CGM has revolutionized the treatment of patients on intensive insulin therapy and its utility can also be harnessed to help individuals with prediabetes make healthful lifestyle changes. Successful weight loss requires adherence to lower calories, regular exercise, and self-monitoring.³ **This proposal will test the hypothesis that RT-CGM will facilitate all of these components for successful weight loss by functioning as a continuous self-monitor and guiding healthful food choices and physical activity.**

Overweight/obese patients with prediabetes will be randomized to intermittent RT-CGM with dietitian support (n=25) versus dietitian support only (n=25). The CGM group will wear the RT-CGM for 10 days at baseline, months 1 and 2. The baseline RT-CGM will be the “learning phase” to teach effects of usual food intake and activity on glucose levels. The subsequent CGM trials will be used to enforce healthful eating and at least 150-min of moderate intensity exercise to maintain normal peak glucose less than 140 mg/dL (“enforcement phase”).

2. STUDY AIMS

If any of the primary or secondary outcome measures are changed, study staff must update clinicaltrials.gov.

The primary objective will be to determine whether intermittent use of a RT-CGM will facilitate weight loss in individuals who are overweight/obese with prediabetes.

2.1. Primary Outcome Measure

AIM #1: Compare weight loss.

Intermittent RT-CGM use will augment dietitian-guided weight loss in individuals with prediabetes.

2.2. Secondary Outcome Measure

AIM #2: Compare physical activity.

Intermittent RT-CGM use will increase physical activity compared with dietitian support only.

Other measures will include glucose indices (fasting glucose, A1c).

3. STUDY DESIGN

3.1 Sample Size

We aim to have 50 total participants in this study.

3.2 Study Population

We aim to enroll 50 participants who are overweight/obese with prediabetes. Please see [APPENDIX A](#) for more detailed inclusion/exclusion criteria.

3.3 Study Location

Participants will be recruited from the San Francisco Bay Area. The research study office is located near the Stanford Hospital and Clinics at [name].

Blood draws will occur in the Boswell Clinic Laboratory at [name].

3.4 Study Duration

We anticipate that the entire study will take 24 months through data analysis.

Months 1-3

-Prepare IRB and study protocols

Months 4-14

-Recruit 5 individuals per month

Months 14-18

-Last group of participants completes protocol

Months 18-24

-Data cleaning

-Data analysis

3.5 Randomization

Eligible participants will be consented for the study and have baseline measurements before being randomized to either the RT-CGM versus dietitian only group. Participants will be randomized according to a computerized random number generator.

4. STUDY PROCEDURES

4.1 Study Design

This will be a randomized, parallel-group, pilot study of intermittent RT-CGM with dietitian support versus dietitian support only. We will randomize 50 individuals who are overweight/obese (BMI 25-40 kg/m²) with prediabetes. A registered dietitian will meet with all volunteers monthly for 3 months and advise on a hypocaloric diet (500 kcal/day deficit) and physical activity (150 minutes per week). (See Fig 2).

4.2 Recruitment

Preliminary recruitment strategies will include:

[figure not shown]
- Recruitment through the Endocrinology Clinic.
- Targeted mass mailings from existing study participants lists (individuals who expressed interest in participating in future studies) and other email lists, currently over 10,000 emails.

Pace of recruitment will be monitored throughout the study. Since the recruitment timeline can be difficult to predict, if the pace is significantly slower than anticipated, the Primary Investigators may decide to alter the budget, timeline, and/or elements of study design (e.g., alter enrollment target, increase budget, reduce elements of data generation) accordingly.

4.3 Intervention

Participants will be randomized 1:1 to either the CGM group with dietitian support or Dietitian-only group (See Fig 2). At baseline, patients in the CGM group will wear a Dexcom RT-CGM for 10 days and be advised to keep a food and activity log for 7 days (This will be the “learning phase”). They will then meet with a registered dietitian to review CGM and food/activity log and be advised on a 500 kcal deficit diet and 150 min/week physical-activity goal. They will also be advised to target postprandial glucose less than 140 mg/dL. They again will wear CGM for 10 days followed by dietitian consultation at months 1 and 2 (“enforcement phase”).

Volunteers randomized to Dietitian-only group will meet with a dietitian at baseline, months 1 and 2. They will also be advised to keep a food and activity log for 7 days prior to meeting with the dietitian. They also will be advised on a 500 kcal deficit diet and 150 min/week physical-activity goal.

Months	0	1	2	3
RT-CGM (in Group 1 only)	X ^{learning}	X ^{enforcement}	X ^{enforcement}	
Dietitian	X	X	X	
Fasting glucose/A1c	X			X
Weight	XX	X	X	X
Physical Activity Review	X	X	X	X
Food Log Review	X	X	X	

Fig 2. Protocol Overview

5. STATISTICAL CONSIDERATION

5.1 Statistical Basis for Sample Size

The primary endpoint will be amount of weight lost in RT-CGM vs Dietitian-only group. Based on a previous weight-loss study of overweight/obese individuals with prediabetes,¹⁶ with 50 participants, we anticipate detecting a within group difference in weight of 1.8 kg and between group difference of 8kg with 80% power and type 1 error of 0.05. Drop out of 20% will result in effect sizes of 2 and 9kg, respectively.

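### The within-group (1.8 and 2 kg) and between-group (8 and 9 kg) detectable differences in section 5.1 cannot both come from one SD of weight lost

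*Combined protocol and SAP*

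**What the plan says.** Section 5.1 (Statistical Basis for Sample Size) defines the endpoint: "The primary endpoint will be amount of weight lost in RT-CGM vs Dietitian-only group". Citing an earlier weight-loss study and taking 50 participants and a type 1 error of 0.05, it continues: "we anticipate detecting a within group difference in weight of 1.8 kg and between group difference of 8kg with 80% power". It then adds: "Drop out of 20% will result in effect sizes of 2 and 9kg, respectively".

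Section 4.3 gives the allocation: "Participants will be randomized 1:1 to either the CGM group with dietitian support or Dietitian-only group". The Study Rationale in section 1 puts 25 people in each arm, so 20% drop-out leaves 20 per arm and 40 in all.

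Section 5.1 gives no SD, test, sidedness or number of people behind the within-group figure. Section 5.2, where the analysis would be described, is marked as still in progress.

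**The concern.** If the endpoint is weight lost, both figures concern the same variable: each person's change in weight. The within-group figure is a one-sample (paired) test on that change, and the between-group figure is a two-sample test on it. Both are multiples of the same SD, so their ratio is fixed by the sample sizes alone. A between-group figure more than four times the within-group figure is far larger than these sample sizes allow.

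This is the plan's only power statement for the primary endpoint, and its possible corrections point in opposite directions. Either the trial is considerably more sensitive than stated, or it has little power for any difference much below 8 kg. The second reading would be a severe limitation. An extra loss of 8 kg exceeds the whole 7% loss that the Background credits to the pivotal prevention trial for anyone under 8/0.07 = 114 kg. It exceeds the 4% average loss in real-life programmes for anyone under 8/0.04 = 200 kg. A reader of a null result needs to know which case applies.

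**Working it through.** **Inputs.** 25 per arm (section 1), 20 per arm after 20% drop-out; 80% power, type 1 error 0.05, and differences of 1.8, 2, 8 and 9 kg (section 5.1). Assumptions, because the plan is silent: two-sided, unadjusted t-tests with a common SD. The number behind the within-group figure is taken as one arm (25, then 20) or everyone (50, then 40).

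**Multipliers.** Detectable difference = d × SD, where d is the standardised difference with 80% power under the noncentral t distribution.

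| Test | n | d |
|---|---|---|
| Two-sample | 25 per arm | 0.8087 |
| Two-sample | 20 per arm | 0.9091 |
| Paired | 25 | 0.5840 |
| Paired | 20 | 0.6604 |
| Paired | 50 | 0.4042 |
| Paired | 40 | 0.4543 |

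**The plan's drop-out step reproduces within each pair.**
- Between groups: 8 × 0.9091/0.8087 = 8.99 kg, stated as 9.
- Within group: 1.8 × 0.6604/0.5840 = 2.04 kg, or 1.8 × 0.4543/0.4042 = 2.02 kg, stated as 2.

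**Implied SD (difference divided by d).**
- Between groups: 8/0.8087 = 9.89 kg; 9/0.9091 = 9.90 kg.
- Within group, one arm: 1.8/0.5840 = 3.08 kg; 2/0.6604 = 3.03 kg.
- Within group, everyone: 1.8/0.4042 = 4.45 kg; 2/0.4543 = 4.40 kg.

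**Ratio check, which needs no SD.**
- Required: 0.8087/0.5840 = 1.38 (one arm) or 0.8087/0.4042 = 2.00 (everyone).
- Stated: 8/1.8 = 4.44 and 9/2 = 4.50.
- Rounding: the lowest ratio that 8 and 1.8 allow is 7.5/1.85 = 4.05. For 9 and 2, with 2 read as a whole number, it is 8.5/2.5 = 3.4.
- One-sided tests throughout: d = 0.7134, 0.5119 and 0.3566, so the required ratios are 1.39 and 2.00.
- Two-sided between and one-sided within: 0.8087/0.5119 = 1.58 and 0.8087/0.3566 = 2.27.

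No variant reaches the stated ratio. Because each pair is coherent over drop-out, the conflict lies between the pairs: they use different SDs.

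**If the within-group figures are right.**
- Detectable between-group difference at 25 per arm: 3.08 × 0.8087 = 2.49 kg, or 4.45 × 0.8087 = 3.60 kg.
- At 20 per arm: 3.08 × 0.9091 = 2.80 kg, or 4.40 × 0.9091 = 4.00 kg.
- The stated 8 kg is then too large by a factor of 8/2.49 = 3.21 or 8/3.60 = 2.22 (2.93 to 3.51, or 2.03 to 2.43, with rounding).

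**If 9.9 kg is the SD of weight change.** The 8 and 9 kg stand. The within-group figures should be 9.9 × 0.5840 = 5.8 kg and 9.9 × 0.6604 = 6.5 kg (one arm), or 9.9 × 0.4042 = 4.0 kg and 9.9 × 0.4543 = 4.5 kg (everyone).

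**What each SD means for the comparison.** The 95% CI half-width is t × SD × √(2/n), with t the 97.5% point on 2n − 2 degrees of freedom.

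| SD of change | Power for 2.5 kg, 25 / 20 per arm | CI half-width, 25 / 20 per arm |
|---|---|---|
| 3.08 kg | 80% / 71% | 1.75 / 1.97 kg |
| 4.45 kg | 49% / 41% | 2.53 / 2.85 kg |
| 9.9 kg | 14% / 12% | 5.63 / 6.34 kg |

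**The case against.** The strongest reply is that no arithmetic slip has been shown. Section 5.1 never says that both pairs share an SD, and all four figures follow from one set of assumptions. Suppose body weight has an SD of 9.89 kg and baseline and final weights correlate at 1 − 3.08²/(2 × 9.89²) = 0.95. The SD of change is then 3.08 kg, which gives 1.8 and 2 kg within group, while a comparison of body weight itself gives 8 and 9 kg between groups. This is plausible, though nothing printed confirms it. It does not rescue the statement: 8 and 9 kg would then be detectable differences in body weight, not in the endpoint that the same section names.

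Other escapes fail. Unequal arm SDs would need about 3.1 kg in one arm and √(2 × 9.89² − 3.08²) = 13.6 kg in the other, which nothing in the documents supports. Adjusting the between-group test for baseline would lower its residual SD, and so lower the required ratio further.

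Three points do stand. The SD may be in the cited study, which was not available here, so this check cannot say which pair is wrong. Reading the within-group figure as all 50 people is a strained meaning of the term and is kept only as a bound. And this is a pilot: section 5.1 reports what 50 participants can detect and does not derive 50 from a target effect. If the within-group figures are right, the stated 8 kg errs on the cautious side.

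**Conclusion.** The concern holds. No single SD of weight lost gives both pairs, so at least one is wrong for the stated endpoint. The stated between/within ratio exceeds the required one by a factor of 4.44/1.38 = 3.2, or 4.44/2.00 = 2.2 on the more lenient reading.

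The between-group difference detectable with 25 per arm is therefore unsettled: about 2.5 kg (3.6 kg on the lenient reading) or 8 kg. These kilogram values are back-solved from the plan's own figures and assume an unadjusted two-sided t-test with equal SDs. The existence of the conflict does not depend on sidedness, rounding or the within-group n.

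This should be fixed, because the only power statement for the primary endpoint cannot be relied on and section 5.2 offers nothing to resolve it. The planned sample size and the conduct of the trial are not affected.

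**What to change.** In section 5.1:

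1. State one SD of weight change with its source, the test, its sidedness, and the number of people behind each figure.
2. Recompute both pairs from that SD and replace whichever is wrong. For an unadjusted two-sided two-sample t-test, the between-group figure is 0.81 × SD at 25 per arm and 0.91 × SD at 20 per arm. Any other test, such as one adjusted for baseline weight, needs its own multiplier.
3. Rest the Aim 1 power statement on the between-group comparison of weight change. Both arms receive the dietitian programme, so a within-group loss does not isolate the effect of the monitor.

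For checking only, and not as sourced targets: expect 2.5 to 3.6 kg (25 per arm) and 2.8 to 4.0 kg (20 per arm) if the within-group figures are right, or 8 and 9 kg if 9.9 kg is confirmed as the SD of weight change.

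The cost is a rewording of section 5.1, with no change to sample size or procedures.

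### The 8 kg (9 kg after drop-out) between-group detectable difference in section 5.1 does not fit the declared endpoint of weight lost: it implies an SD two to three times that implied by the 1.8 kg in the same sentence, and it is not credible as the added effect of CGM

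*Combined protocol and SAP*

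**What the plan says.** Section 2 gives the objective: "The primary objective will be to determine whether intermittent use of a RT-CGM will facilitate weight loss" in overweight or obese people with prediabetes. Section 5.1 defines the endpoint: "The primary endpoint will be amount of weight lost in RT-CGM vs Dietitian-only group". That is a change, and the schedule in section 4.3 measures weight twice at month 0 and then at months 1, 2 and 3.

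The sample size is 50 (section 3.1), and section 4.3 states: "Participants will be randomized 1:1 to either the CGM group with dietitian support or Dietitian-only group". Section 5.1 then says "we anticipate detecting a within group difference in weight of 1.8 kg and between group difference of 8kg with 80% power", with a type 1 error of 0.05. It adds that 20% drop-out raises the two figures to 2 and 9 kg. It names a previous weight-loss study as the basis but gives no SD, and it does not say whether the between-group figure concerns weight change or attained weight. The statistical plan in section 5.2 is marked as still in progress.

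On the treatment contrast, section 4.1 says: "A registered dietitian will meet with all volunteers monthly for 3 months and advise on a hypocaloric diet (500 kcal/day deficit"), together with a goal of 150 minutes of activity a week. Section 4.3 gives this advice to both arms. On the size of loss to expect, the background reports that real-life programmes modelled on the pivotal prevention study do modestly: "interventions show an average weight loss of 4% and show drop-out rates as high as 50"%.

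**The concern.** Two detectable differences stand in one sentence, for the same sample, power and error rate, yet they are more than fourfold apart. If both refer to weight change, a two-arm comparison with 25 per arm should need a difference only √2 times the within-arm figure, or twice that figure if the within-group analysis pools all 50. It should not need 4.4 times (8/1.8).

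The 8 kg is also hard to credit in itself. Both arms have the dietitian, the calorie deficit and the activity goal, so the between-group difference is only what CGM adds.

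This sentence is the only statistical justification for the primary comparison. As it stands, a reader cannot tell what the trial can detect on its own endpoint, or how precise its estimate will be. With section 5.2 unwritten, nothing else in the protocol settles whether weight change or attained weight will be compared.

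**Working it through.** **Inputs.** From sections 3.1, 4.3 and 5.1: 50 participants, 1:1, so 25 per arm; 20 per arm after 20% drop-out; 80% power; alpha 0.05; detectable differences 1.8 and 8 kg (2 and 9 kg after drop-out). From sections 4.1 and 4.3: 500 kcal/day deficit and 150 min/week activity in both arms for 3 months. Assumptions: a two-sided test (sidedness is not stated) and 91 days for 3 months.

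**1. The plan's own figures.** With no SD given, 8 and 1.8 kg cannot be reproduced, only back-solved. The drop-out step does reproduce: 8 × √(25/20) = 8.94 (8.99 by the t distribution), so 9 kg; 1.8 × √(25/20) = 2.01 (2.04), so 2 kg.

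**2. Implied SDs.** The standardised differences detectable with 80% power (noncentral t) are 0.809 for two arms of 25, 0.909 for two arms of 20, 0.584 for one group of 25 and 0.404 for one group of 50.
- Between groups: 8 / 0.809 = 9.9 kg.
- Within group, one arm of 25: 1.8 / 0.584 = 3.1 kg.
- Within group, all 50 pooled: 1.8 / 0.404 = 4.5 kg.

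The ratio is 9.9/3.1 = 3.2 or 9.9/4.5 = 2.2. Under the normal approximation it is 8/(1.8 × √2) = 3.1 or 8/(1.8 × 2) = 2.2, and alpha, power and sidedness cancel. The mismatch therefore does not depend on the two-sided assumption.

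**3. Between-group difference on the endpoint as defined.** Using the unrounded SDs of 3.08 and 4.45 kg:
- 25 per arm: 3.08 × 0.809 = 2.5 kg; 4.45 × 0.809 = 3.6 kg.
- 20 per arm: 3.08 × 0.909 = 2.8 kg; 4.45 × 0.909 = 4.0 kg.

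**4. Expected 95% confidence-interval half-width**, t × SD × √(2/n):
- 25 per arm (t = 2.011): 1.75 kg and 2.53 kg.
- 20 per arm (t = 2.024): 1.97 kg and 2.85 kg.
- At the SD implied by 8 kg, 25 per arm: 5.6 kg.

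**5. Is 8 kg credible as an increment?** From the documents alone, 8 kg is 4% of 8/0.04 = 200 kg. CGM alone would have to add what the background's average programme achieves in total only in a 200 kg person. The background gives no duration for that 4%.

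In energy terms the documents give no conversion, so this step is an assumption. At 7,000 to 7,700 kcal/kg over 91 days, 8 kg needs 8 × 7,000/91 = 615 to 8 × 7,700/91 = 677 kcal/day beyond the control arm. Widening the assumption to 6,000 to 9,000 kcal/kg gives 527 to 791. All of these exceed the 500 kcal/day prescribed to both arms. Over 120 days (the overview mentions 4 months on study, though the schedule ends at month 3), 7,000 to 7,700 kcal/kg gives 467 to 513 kcal/day, roughly the whole prescribed deficit over again.

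**The case against.** The best defence is that the two figures describe different quantities. The 1.8 kg would be a paired change, and the 8 kg a difference in attained weight, where an SD near 10 kg would reflect spread in body weight between people. Both could then be computed correctly. This is a likely explanation, though an inference. It does not rescue the sentence, because the endpoint is weight lost and baseline weight is measured, so an attained-weight figure answers a different question. If instead 9.9 kg really were the SD of change, the within-group figure would have to be 9.9 × 0.584 = 5.8 kg (n = 25) or 9.9 × 0.404 = 4.0 kg (n = 50). Either way, one number does not belong to this endpoint.

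It can also be said that this is labelled a pilot, and that 8 kg is a difference the investigators anticipate detecting rather than a declared target. Both are fair and limit the criticism to the power statement. For the same reasons, rewording the objective from determining to estimating is a preference and not a needed correction.

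Three stronger readings are tempting, and the documents support none of them.
- A reader might infer that the trial cannot answer its question, with power of only 11 to 21% for a CGM increment of, say, 2.1 to 3.3 kg (3% of an assumed 70 to 110 kg). That holds only if the analysed quantity has an SD of 9.9 kg. On the SDs implied by 1.8 kg, the same increments have power of 66 to 96%, or 37 to 73% on the pooled reading, with 25 per arm.
- A reader might infer that 8 kg exceeds anything the programme could produce in total. Diet alone gives 500 × 91 = 45,500 kcal, or 5.9 to 6.5 kg at 7,700 to 7,000 kcal/kg. Adding the activity goal at an assumed 5 kcal/min brings this to 7.2 to 7.9 kg, and 120 days of diet alone gives 7.8 to 8.6 kg. The claim turns on outside assumptions.
- A reader might take the gap between the background's 4% and the pivotal study's 7% as the margin for judging benefit. The protocol gives these as total losses in different programmes and never as an expected CGM effect.

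**Conclusion.** The point holds as a defect of section 5.1. The 8 and 9 kg figures are inconsistent with the 1.8 and 2 kg beside them by a factor of 2.2 to 3.2 in implied SD, and they are implausible as the increment from CGM. On the endpoint as defined, the same 50 participants would give a detectable difference of about 2.5 to 3.6 kg (2.8 to 4.0 kg with 20 per arm).

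This recalculation assumes a two-sided test and that the 1.8 kg reflects the SD of weight change. The range covers the two readings of the within-group sample. The true SD is not in the documents. The source cited is, by its title, a study of liraglutide in older people with prediabetes, so its SD may not carry over to this programme and should be justified. Even 2.5 to 4.0 kg is a sizeable increment over dietitian support, so limited power for smaller effects remains. That is a limit on precision to be stated openly, and does not show that the design fails.

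**What to change.** In section 5.1:
- State the SD of weight change, its source, whether the within-group figure uses 25 or 50 participants, and the sidedness of the test.
- Replace 8 and 9 kg with the detectable between-group difference in weight change. On the SD implied by 1.8 kg this is about 2.5 to 3.6 kg, or 2.8 to 4.0 kg after drop-out. The range becomes a single figure once the SD is stated.
- Give the expected 95% confidence-interval half-width beside it: about 1.8 to 2.5 kg with 25 per arm and 2.0 to 2.9 kg with 20, on the same SDs.

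In section 5.2, name the primary analysis as the between-group comparison of weight change from baseline to month 3, adjusted for baseline weight and reported with its 95% confidence interval.

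The cost is wording, plus having to disclose the SD. Participants, visits and sample size do not change.
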